### 3.3.4.2. Withdrawal of consent to trial participation

Subjects may withdraw their consent to trial participation at any time without the need to justify the decision. If a subject wants to withdraw consent, the investigator should be involved in the discussion with the subject and explain the difference between trial treatment discontinuation and withdrawal of consent to trial participation, as well as explain the options for continued follow up after trial treatment discontinuation, please see section [3.3.4.1](#) above.

### 3.3.4.3. Discontinuation of the trial by the sponsor

Boehringer Ingelheim reserves the right to discontinue the trial at any time for any of the following reasons:

1. Failure to meet expected enrolment goals overall or at a particular trial site
2. New toxicological findings, serious adverse events, or any safety information invalidating the earlier positive benefit-risk assessment. Dose escalation will be terminated if more than 50% of the subjects at one dose level show drug-related and clinically relevant adverse events of moderate or severe intensity, or if at least one drug-related serious adverse event is reported.

Proprietary confidential information © 2021 Boehringer Ingelheim International GmbH or one or more of its affiliated companies

3. Violation of GCP, or the CTP, or the contract with BI impairing the appropriate conduct of the trial.
4. The sponsor decides to discontinue the further development of the investigational product.
5. Dose escalation will be stopped if at least 1/3 subjects on active treatment at one dose level have relevant individual QT prolongations, i.e. a QTc increase of greater than 60 ms from baseline in connection with absolute QT or QTc greater than 500 ms, as confirmed by a repeat ECG recording.

The investigator / trial site will be reimbursed for reasonable expenses incurred in case of trial termination (except if item 3 applies).

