### Clinical experience

At the time of preparing this trial protocol, three Phase I trials with administration of single doses of BI 1323495 to healthy male volunteers have been completed, trials 1405-0001 was first-in-man trial, 1405-0007 investigated relative BA (Bioavailability) and food effect, and 1405-0009 investigated drug interaction with itraconazole. In addition to this, 1405-0002, multiple rising dose (MRD) trial in healthy subjects is currently ongoing, and analysis of the DDI trial (1405-0015) with Rosuvastatin (BRCP and OATP1B1 substrate) and Dabigatran (P-gp substrate) is ongoing.

In the single rising dose (SRD) trial 1405-0001, single-dose treatment with up to 600 mg BI 1323495 or placebo was safe and well tolerated. There was no relationship between the occurrence of AEs and dose. Three AEs in subjects receiving BI 1323495 were judged as moderate in intensity, all other AEs were classified as mild. No severe or serious AEs were reported. The most frequently reported treatment-emergent AE was headache, reported for 6 out of 48 subjects (12.5%) receiving BI 1323495 and 2 out of 15 subjects (13.3%) receiving placebo. The next-most frequently reported treatment-emergent AEs were fatigue and diarrhea, each reported for 2 out of 48 subjects (4.2%) receiving BI 1323495. In one subject receiving 300 mg BI 1323495, a mild (<2-fold upper limit of normal [ULN]) and transient elevation of alanine transaminase (ALT) and glutamate dehydrogenase (GLDH) was reported.

The level of exposure to BI 1323495 was dependent on the expression pattern of the enzyme UGT2B17 in the intestine. While homozygous and heterozygous carriers of the wild type allele (UGT2B17 \*1/\*1 and \*1/\*2) could not be distinguished based on their exposures, AUCs and  $C_{max}$  were increased in subjects with homozygous deletion of UGT2B17 (\*2/\*2), compared with the other genotypes (Table [1.2.1: 1](#)) [[c26492551](#)].

After the first-pass metabolism, the same pharmacokinetic properties apply to all genotypes. gMean (geometric mean) plasma exposure increased in a less than dose-proportional manner. Multiple plasma concentration peaks were observed in the profiles of nearly all subjects treated. Subjects with genotype \*2/\*2 did not show as many peaks as the other genotypes in the concentration-time profiles. The terminal half-life was similar over all dose groups, except for being longer in the 600 mg dose group.

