### 3. DESCRIPTION OF DESIGN AND TRIAL POPULATION

#### 3.1. OVERALL TRIAL DESIGN AND PLAN

##### SRD part for PM

This single rising dose part is designed as single-blind, randomised, and placebo-controlled within dose groups.

It is planned to include a total of 24 healthy male subjects in the trial part.

The subjects will be assigned to 3 groups consisting of 8 subjects per group; the groups will be dosed sequentially (see Table 3.1: 1). Within each dose group, 6 subjects will receive BI 1323495 and 2 will receive placebo. Only one dose is tested within each dose group.

The trial schedule and design are depicted in Figure 3.1: 1.

Figure 3.1: 1

Trial design “SRD part for PM”

The dose groups to be evaluated are outlined in Table 3.1: 1 below.

Table 3.1: 1 Dose groups for UGT2B17 PM

Dose Group	1	2	3
Dose (mg)	10	30	100
Number of subjects	8	8	8
Subjects receiving placebo	2	2	2
Subjects receiving active drug	6	6	6

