### SRD part for EM

This single rising dose part is designed as single-blind, randomised, and placebo-controlled within dose groups.

It is planned to include a total of 12 healthy male subjects in the trial part.

The subjects will be assigned to 3 groups consisting of 4 subjects per group; the groups will be dosed sequentially (see Table 3.1: 2). Within each dose group, 3 subjects will receive BI 1323495 and 1 will receive placebo. Only one dose is tested within each dose group.

The trial schedule and design is depicted in Figure 3.1: 2.

[figure not shown]

Figure 3.1: 2 Trial design “SRD part for EM”

The dose groups to be evaluated are outlined in Table 3.1: 2 below.

Table 3.1: 2 Dose groups for UGT2B17 EM

Dose Group	1	2	3
Dose (mg)	30	70	150
Number of subjects	4	4	4
Subjects receiving placebo	1	1	1
Subjects receiving active drug	3	3	3

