#### MD part for PM

Single-blind conditions regarding the subject's treatment (active or placebo) are maintained within each dose group. However, subjects and investigators will be aware of the dose of the drug administered. The disadvantage of this trial design is a possible observer bias with regard to the dose-dependent effects; in addition, the sequential dosing of groups could potentially result in time-related effects. However, as such effects are expected to be small relative to the differences between the doses in the broad range investigated, unbiased comparisons between treatments can still be expected.

It is standard in multiple dosing trials involving healthy volunteers to include a placebo group to control for safety and tolerability of the trial medication. In the MD part, each dose group consists of 12 subjects, with 9 on active treatment, and 3 on placebo. 9 subjects per active treatment group in the MRD part, is considered to be sufficient for the exploratory evaluation of safety, pharmacokinetics, and pharmacodynamics.

The treatment period of 11 days is considered adequate for collection of safety, pharmacokinetic, and pharmacodynamic data after multiple dosing at steady state to inform subsequent studies along the clinical development path. The treatment period is adequately covered by non-clinical toxicology data from animal studies.

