#### **4.1.4. Drug assignment and administration of doses for each subject**

The treatments to be evaluated are outlined in Tables [4.1.4: 1](#), [4.1.4: 2](#) and [4.1.4: 3](#). The number of tablets for placebo corresponds to the number of tablets in the corresponding dose level.

Proprietary confidential information © 2021 Boehringer Ingelheim International GmbH or one or more of its affiliated companies

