#### **4.1.5. Blinding and procedures for unblinding**

##### **4.1.5.1. Blinding**

### ***SRD and MD part***

SRD and MD part is designed single-blind. The treatments administered (active or placebo) will be blinded to subjects, but will be known to the investigators (outcome assessors). Only the current dose level will be known to the subjects due to the rising dose design.

Proprietary confidential information © 2021 Boehringer Ingelheim International GmbH or one or more of its affiliated companies

A single-blind design is considered acceptable because the potential bias in this type of trial seems to be low and according to trial procedures it is assured that the investigator's knowledge of the next treatment does not influence the decision to enter a subject.

All trial data will be handled open label. This means that trial functions of the sponsor are unblinded (including clinical trial manager (CTM), data manager, statistician, bioanalyst, pharmacokineticist, pharmacometrist, drug metabolism scientist as well as dedicated personnel of the trial site).

Access to the randomisation schedule will be controlled and documented by a signed confidentiality statement, which will be stored in the TMF.

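### The adverse-event stop for dose escalation does not limit its count to subjects on active drug, as the QT stop in the same section does

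*Protocol*

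**What the plan says.** Protocol Section 3.3.4.3 lists two numerical stops for dose escalation.

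- Item 2: "Dose escalation will be terminated if more than 50% of the subjects at one dose level show drug-related and clinically relevant adverse events". Only events graded moderate or severe count. The same item also ends escalation after a single drug-related serious adverse event.
- Item 5: "Dose escalation will be stopped if at least 1/3 subjects on active treatment at one dose level have relevant individual QT prolongations".

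The dose groups are mixed. For SRD in PM, "Within each dose group, 6 subjects will receive BI 1323495 and 2 will receive placebo". For SRD in EM, "Within each dose group, 3 subjects will receive BI 1323495 and 1 will receive placebo". For MD, "each dose group consists of 12 subjects, with 9 on active treatment, and 3 on placebo".

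Section 3.1 (Dose escalation and safety review) allows a review once data are available from two thirds of the subjects on active drug. It makes escalation a joint decision of the Principal Investigator, the clinical trial leader and the Team Member Medicine, who must all see no safety concern. Both the escalation condition and the list of data to review refer to Section 3.3.4.1 for stopping criteria.

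**The concern.** Item 5 and the minimum-data rule in Section 3.1 both name the active subjects as their base. Item 2 does not, although it sits in the same list as item 5. A literal reader therefore counts everyone in the dose group. Placebo subjects are not expected to have drug-related events, so counting them dilutes the share and raises the number of affected active subjects needed to stop.

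The groups are small, so one subject more or less decides the matter. In an EM group, the literal rule would need all three dosed men to be affected if the placebo subject is not. A mandatory numerical safety stop should have one reading, and it should measure harm among those exposed to the drug.

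**Working it through.** **Is the denominator defined anywhere?** No protocol or SAP section defines it. Two places bear on what a dose level covers. Section 4.1.4: "The number of tablets for placebo corresponds to the number of tablets in the corresponding dose level". Section 4.1.5.1: "Only the current dose level will be known to the subjects due to the rising dose design". The second applies to all blinded subjects, placebo included. In the other direction, Section 7.3.4 pools SRD placebo subjects into one comparison group, and SAP Table 6.1: 1 gives placebo its own label. The text does not settle the question.

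**Trigger counts.** The plan states none, so there is no figure to reproduce. The group sizes agree with the planned totals: 3 × 8 = 24, 3 × 4 = 12, 2 × 12 = 24. The smallest count above 50% of n is r = floor(n/2) + 1. If x placebo subjects have qualifying events, the literal rule needs r − x active subjects.

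| Group | Active + placebo | Literal trigger | Active needed, x = 0 | Active needed, x = 1 | Active-only trigger |
|---|---|---|---|---|---|
| PM SRD | 6 + 2 | 5 of 8 | 5 of 6 (83%) | 4 of 6 | 4 of 6 (67%) |
| EM SRD | 3 + 1 | 3 of 4 | 3 of 3 (100%) | 2 of 3 | 2 of 3 (67%) |
| MD | 9 + 3 | 7 of 12 | 7 of 9 (78%) | 6 of 9 | 5 of 9 (56%) |

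With x = 0 the readings disagree at 4 of 6 (PM), 2 of 3 (EM), and 5 or 6 of 9 (MD). Placebo events can also push the other way. In a PM group, 3 active plus 2 placebo events give 5/8 = 62.5% (stop), but 3/6 = 50% on active (no stop).

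**Chance that this one rule trips.** Exact binomial over active subjects, placebo rate 0: P = Σ from k = r to n of C(n,k) pᵏ(1−p)ⁿ⁻ᵏ. For example, EM at p = 0.4: literal 0.4³ = 0.064; active-only 3 × 0.4² × 0.6 + 0.4³ = 0.352.

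| Assumed p | PM literal / active-only | EM literal / active-only | MD literal / active-only |
|---|---|---|---|
| 6.25% | 0.0005% / 0.02% | 0.02% / 1.1% | <0.0001% / 0.01% |
| 20% | 0.2% / 1.7% | 0.8% / 10.4% | <0.1% / 2.0% |
| 40% | 4% / 18% | 6% / 35% | 2.5% / 27% |
| 60% | 23% / 54% | 22% / 65% | 23% / 73% |

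The first rate is 3/48 from the earlier single-dose trial (Section 1.2.1): "Three AEs in subjects receiving BI 1323495 were judged as moderate in intensity, all other AEs were classified as mild", with 48 subjects on active drug and no severe event. It ignores causality, so it is the most that trial could show for qualifying events. The 20% row is close to 11/56 = 19.6%, the share with a drug-related event of any intensity in the ongoing multiple-dose trial. The 40% and 60% rows are hypothetical.

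**Review on partial data.** Two thirds of 6, 3 and 9 active subjects is 4, 2 and 6. More than 50% of those is 3 of 4, 2 of 2 and 4 of 6. Suppose instead that placebo counts, all placebo data are in with no qualifying event, and every reviewed active subject is affected. Over the full group the share is 4/8 = 2/4 = 6/12 = 50% (no stop). Over subjects with data it is 4/6 = 2/3 = 6/9 = 67% (stop). Item 2 does not say which base applies.

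**The case against.** The strongest reply is that the count is only a backstop. Section 3.1 lets the next group be treated only if no safety concern has arisen and no dose-limiting event has occurred. Section 4.1.5.1 leaves investigators and sponsor staff unblinded. A review team that knows 4 of 6 or 2 of 3 active subjects had moderate or severe drug-related events would be hard put to see no concern. Item 2 itself also lets the sponsor stop on any safety information that overturns the benefit-risk assessment. This stands, and it limits the harm.

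It can also be said that active-only is the natural reading: the protocol's usual term for a cohort with placebo is dose group, the tablet sentence in Section 4.1.4 could set placebo apart from the dose level, and unblinded investigators judge causality. That is fair, and the documents do not show that the sponsor meant placebo to count. But item 5 shows that the sponsor writes the limit when it is wanted, so the omission leaves a literal reading open.

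Finally, the documented rates are low. At 6.25% the rule trips at most 1.1% of the time under either reading. That figure comes from fasted single doses with 41 of 48 subjects EM, so it transfers imperfectly to fed PM dosing. Even so, the documents give no reason to expect the rates at which the readings differ most.

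**Conclusion.** The point holds as a minor one. Item 2 as worded admits a less protective trigger than the active-only rule whenever no placebo subject has a qualifying event: one more affected active subject in an SRD group, two more in an MD group. The condition matters. With one qualifying placebo event the two SRD triggers coincide, and such an event is possible: in the earlier multiple-dose trial, 1 of 19 placebo subjects had a severe event judged related (Section 1.2.1).

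A reader might infer more than the documents support:

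- That escalation would go ahead with 4 of 6 or 2 of 3 active subjects affected. The joint safety judgement stands in the way, so the percentages above are chances that one rule trips, not chances that escalation stops.
- That the stop is not in force because Section 3.1 refers only to Section 3.3.4.1, which holds individual discontinuation criteria. Item 2 binds by its own wording, so the cross-reference is an editorial matter.

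The rule matters mainly for the SRD steps. Both MD groups receive 60 mg a day, although predicted steady-state Cmax is higher for once-daily dosing (496 against 350 nM, Section 4.1.2).

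**What to change.** In Section 3.3.4.3 item 2, insert *on active treatment* after *subjects*, as in item 5. State the full-group counts: 4 of 6 (PM SRD), 2 of 3 (EM SRD), 5 of 9 (MD).

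Add one sentence saying that, at a review on partial data, the 50% applies to active subjects with data. At the two-thirds minimum this means 3 of 4, 2 of 2 and 4 of 6. Do not carry the full-group counts over to a partial review: they would require 4 of 4 (PM) and 5 of 6 (MD), so 3 of 4 affected PM subjects (75%) would not trip the rule.

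As an editorial correction, add Section 3.3.4.3 to the stopping-criteria references in the Section 3.1 escalation condition and review list.

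The cost is a few words, one or two sentences and the added cross-references. Sample size, visits and data collection are unchanged.

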### **3.3.5. Replacement of subjects**

In SRD and MD part, if some subjects do not complete the trial, or there is not a sufficient number of subjects on active within one dose group the Trial Clinical Leader together with the Trial Pharmacokineticist and the Trial Statistician are to decide, if and how many subjects will be replaced. In DDI part, if more than 2 subjects do not complete the trial, the CTL together with the Trial Pharmacokineticist and the Trial Statistician are to decide, if and how many subjects will be replaced. A replacement subject will be assigned a unique trial subject number, and will be assigned to the same treatment as the subject he replaces.

## **4. TREATMENTS**

### **4.1. INVESTIGATIONAL TREATMENTS**

The investigational product BI 1323495 as tablet formulation has been manufactured by BI Pharma GmbH & Co. KG. Itraconazole oral solution will be prepared by a site pharmacy department.

#### **4.1.1. Identity of the Investigational Medicinal Products**

The characteristics of the test product are given below:

##### Test product 1

Substance: BI 1323495  
Pharmaceutical formulation: Tablet, film-coated  
Source: BI Pharma GmbH & Co. KG, Germany  
Unit strength: 10 mg and 50 mg  
Posology: 1-0-0 and 1-0-1 (30 mg bid only)  
Route of administration: Oral  
Duration of use: SRD part: Single dose  
MD part: 11 days  
DDI part: Single dose for each treatment R and T

##### Test product 2

Name: ITRIZOLE® Oral Solution 1% [REDACTED]  
Substance: Itraconazole  
Pharmaceutical formulation: Oral solution  
Source: Site pharmacy department  
Holder of marketing authorisation: [REDACTED]  
Unit strength: 10 mg/mL  
Posology: 20 mL-0-0  
Route of administration: Oral  
Duration of use: 10 days in treatment T

The characteristics of the reference product (placebo) are given below:

Substance: Placebo

Pharmaceutical formulation: Tablet, film-coated

Source: BI Pharma GmbH & Co. KG, Germany

Unit strength: Not applicable

Posology: 1-0-0 and 1-0-1 (30 mg bid only)

Route of administration: Oral

Duration of use: SRD part: Single dose

MD part: 11 days

DDI part: Sing dose for each treatment R and T

#### 4.1.2. Selection of doses in the trial and dose modification

##### ***SRD part***

The doses selected for this trial are assumed to cover the therapeutic dose.

##### Maximum dose for each UGT2B17 genotype group

The maximum doses are 100 mg and 150 mg under fed condition for UGT2B17 PM and EM, respectively. The human exposure caps are a  $C_{max}$  gMean value of 1900 nM and  $AUC_{0-24}$  gMean value of 11500 nM·h [[c21238478-05](#)]. For the current trial,  $C_{max}$  gMean and  $AUC$  gMean are predicted to be below the exposure cap and not to exceed exposures that were already achieved (maximum values of  $C_{max}$  and  $AUC_{0-24}$  were 717 nM and 6790 nM·h, respectively) and considered safe in individual PM subjects participating in the first-in-human trial 1405-0001. The expected margins versus human exposure caps (Table 4.1.2: 1) are considered reasonable; therefore, single administration of the maximum dose in each UGT2B17 genotype group are considered safe.

Table 4.1.2: 1 Predicted PK parameters for the maximum dose group in each UGT 2B17 genotype group after single dose administration of BI 1323495 in the fed state

	AUC 0-24		AUC 0-∞		$C_{max}$	
	Model Prediction (gMean)	Exposure multiple	Model Prediction (gMean)	Exposure multiple	Model Prediction (gMean)	Exposure multiple
UGT 2B17 PM						
100 mg	4380	2.6	7210	1.6	374	5.1
UGT 2B17 EM						
150 mg	1620	7.1	2610	4.4	142	13

Model prediction: Single dose, tablet formulation, fed condition, Male, Mean body weight 65 kg, UGT 2B17 genotype (PM or EM)

Exposure multiple: calculated as ratio of predicted exposure to exposure cap ( $AUC_{0-24,ss}$ : 11500 nM·h,  $C_{max,ss}$ : 1900 nM)

### MD part

In this part, 30 mg bid and 60 mg qd under fed condition is selected as the dose to be tested for UGT2B17 PM. The human exposure caps are a  $C_{max}$  gMean value of 1900 nM and  $AUC_{0-24}$  gMean value of 11500 nM·h [[c21238478-05](#)]. For the current trial,  $C_{max}$  gMean and  $AUC$  gMean are predicted to be below the exposure cap. In addition, multiple doses of BI 1323495 investigated, including UGT2B17 PM 10 mg bid and 30 mg bid group, so far in clinical trials with healthy subjects were safe and well tolerated (please see Section [1.2.1](#) in detail); therefore, multiple administrations of 30 mg bid and 60 mg qd in UGT2B17 PM group are considered safe.

Table 4.1.2: 2 Predicted PK parameters for 30 mg bid and 60 mg qd in UGT 2B17 PM genotype group after multiple dose administrations of BI 1323495 in the fed state

	$AUC_{0-24,ss}$		$C_{max,ss}$	
	Model Prediction (gMean)	Exposure multiple	Model Prediction (gMean)	Exposure multiple
UGT 2B17 PM				
30 mg bid	6160	1.9	350	5.4
60 mg qd	6010	1.9	496	3.8

Model prediction: bid: twice daily, qd: once daily, assuming tablet formulation, fed condition, Male, Mean body weight 65 kg, UGT 2B17 genotype (PM)

Exposure multiple: calculated as ratio of predicted exposure to exposure cap ( $AUC_{0-24,ss}$ : 11500 nM·h,  $C_{max,ss}$ : 1900 nM)

### DDI part

#### Perpetrator (itraconazole)

The dose of itraconazole selected for this trial reflects standard clinical doses, is considered sufficient to yield significant CYP3A and P-gp inhibition, and has been used successfully and safely in previous drug-drug-interaction trials ([c02336088](#), [c03355329](#), [c08928447](#), [c27223001](#)).

#### Victim (BI 1323495)

For the current trial, a dose of 10 mg BI 1323495 under fasted condition is selected, which is same to that tested in trial 1405-0009. The predicted exposure of a dose 10 mg BI 1323495 alone under fasted condition in UGT2B17 PM is displayed in Table [4.1.2: 2](#). The exposure multiples of  $C_{max}$  and  $AUC$  were 32 and 12-19, respectively.

In trial 1405-0001, in the 200 mg dose group - the dose group with highest mean exposures - gMean values for  $C_{max}$  and  $AUC_{0-24}$  were 229 nM and 2390 nM·h, respectively.

([c26492551](#)). The ratios of these gMean plasma exposure parameters at the 200 mg dose group to the predicted exposure for the current trial ( $C_{max}$ : 59.9 nM,  $AUC_{0-24}$ : 609 nM·h) are approximately 4.

The victim potential of BI 1323495 upon inhibition of CYP 3A4 / P-pg in UGT2B17 EM has already been assessed in trial 1405-0009, suggesting that a modest increase in exposure to BI 1323495 in gMean  $AUC_{0-\infty}$  and  $C_{max}$  of 1.69- fold and 1.37-fold, respectively, occurs

Proprietary confidential information © 2021 Boehringer Ingelheim International GmbH or one or more of its affiliated companies

when BI 1323495 10 mg single administered together with itraconazole. UGT2B17 PM, when treated with a strong inhibitor of CYP 3A4 and P-gp such as itraconazole, lack two main metabolic pathways and may experience a more pronounced effect of CYP 3A / P-gp inhibition of exposures to BI 1323495. The predicted exposure after single dose administration of 10 mg BI 1323495 alone and with 200 mg itraconazole in UGT2B17 PM by PopPK model based on the clinical trials (1405-0001 and 1405-0007) are shown in Table 4.1.2: 2. In this simulation, the inhibition effect by itraconazole on PK of BI 1323495 mainly affects the bioavailability but not the elimination which was observed in UGT2B17 EM in trial 1405-0009. From this simulation, the exposure multiple of the predicted exposure with itraconazole in UGT2B17 PM are more than 5 and the predicted exposure are still lower than that experienced in trial 1405-0001. Considering these findings, it is considered to be safe for increases of BI 1323495 plasma exposures in UGT 2B17 PM when 10 mg BI 1323495 administered given together with itraconazole.

Table 4.1.2: 3 Predicted PK parameters after 10 mg BI 1323495 single administration under fasted condition (BI 1323495 alone and with itraconazole)

	AUC 0-24		AUC 0-∞		C max	
	Model Prediction (gMean)	Exposure multiple	Model Prediction (gMean)	Exposure multiple	Model Prediction (gMean)	Exposure multiple
UGT 2B17 PM						
10 mg	609	19	963	12	59.9	32
10 mg + 200 mg itraconazole	1260	9.1	2000	5.8	121	16

Model prediction: Single dose, tablet formulation, fasted condition, Male, Mean body weight 65 kg, UGT 2B17 PM  
Exposure multiple: calculated as ratio of predicted exposure to exposure cap (AUC0-24,ss: 11500 nM·h, Cmax,ss: 1900 nM)

